Confirmation is provided by the Per Protocol (PP) population analysis in which the combined RBX2660 treatment groups A and C with a success rate of 75.0% (45/60) were compared to the placebo 52.9% (18/34) with a significant p-value of 0.029 by Pearson's chi-square during the blinded treatment phase. Further, overall RBX2660 efficacy rate in PP subjects who received at least 1 RBX2660 enema either blinded or in open label (n=76) was 93.4% (71/76). When compared to the PP Control Group B rate of 52.9%, a resulting p-value of <0.0001 further substantiates that RBX2660 is an effective treatment for the prevention of recurrent CDI.

Overall the efficacy data confirms the following primary conclusions:

- Treatment with RBX2660 following a standard course of antibiotics significantly increases the success rate for prevention of recurrent *Clostridium difficile* infection in subjects with a history of multi-recurrent disease.
- Appropriate treatment with RBX2660 includes a single enema administered following completion of a standard course of antibiotics with another RBX2660 enema administered only if CDI symptoms return.

Not only do these results prevent a recurrence of CDI within the 56 day (8 week) timeline as established by the CDC, the results are maintained longer term. The long term CDI free rate at the time of this analysis was 95.8% (91/95) for subjects successfully treated with RBX2660 at an average follow-up of 8.2 months (range: 1.6 – 14.9).

Lastly, the donor screening and manufacturing process appears to properly ensure the quality of the RBX2660 product as consistent results in treatment success are shown regardless of donor.

These efficacy results also validate previous results from the Phase 2 study which reported an 87.1% treatment success with RBX2660.

SAFETY RESULTS: The Safety Population (SP) consists of any subject who had a study enema attempted (n=128) whether placebo or RBX2660. Adverse events were independently reviewed by a Medical Monitor with additional oversight by a DSMB for evaluation of safety trends and stopping rules. The DSMB completed an interim review of safety data as reported during the double-blind period. Following review, the DSMB recommends continuation of the study as no pre-defined study stopping rules have been met or other safety concerns identified.

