4.3 Method of Assignment of Subjects to Treatment Arms

After enrollment and confirmation of inclusion/exclusion criteria compliance, randomization occurs via the study database with blinded treatment occurring within 14 calendar days of randomization. The randomization assignment is transmitted only to the Rebiotix Operations Department, who will ship the correct IP to the site for each treatment. Subjects are considered enrolled once they sign the informed consent form.

Trained and authorized study personnel will access the centralized randomization system to randomize the subject to one of the available treatment arms. The randomization schedule will be created using randomized blocks within four strata based on antibiotics used at screening (Vancomycin alone, Vancomycin in combination, Fidaxomicin or Other), and randomized subjects will be assigned one of two treatments (Group A or Group B) within the appropriate

stratum. The randomization will not be stratified by site, so each site will draw from the same set of blocks. A subject will be assigned the next available treatment allocation from the randomization list. The randomization code and the date and time of randomization will be captured in the clinical database. Randomization will be in a 2:1 ratio with approximately 2 subjects randomized to active treatment for every 1 subject randomized to placebo.

Enrolled subjects who are exited prior to randomization or are randomized but exited prior to attempting the blinded treatment may be re-enrolled and thus randomized under a different subject identification numbers (re-randomized). If this occurs, they will be included in the analysis using their second randomization assignment and subsequent assessments and will only be counted once towards the total number randomized.

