6.4.2 Secondary Efficacy Endpoint

The secondary efficacy endpoint is the recurrence of CDI through 6 months after blinded treatment. This will be analyzed as the difference in time to CDI event between RBX2660 and Placebo following blinded treatment through 6 months of follow-up. This analysis will only be

analyzed if statistical significance ($p < 0.05$) is demonstrated for the primary efficacy endpoint. These endpoints will be tested at a two-sided 0.05 significance level.

The null hypothesis of interest is that there is no difference between RBX2660 and Placebo treated subjects in the probability of CDI at any time point during the 6 months of follow-up. The alternative is that there is a difference in the probability of CDI at any time point during 6 months of follow-up.

The power to detect the difference between RBX2660 and Placebo treatment at 6 months was estimated by 10,000 simulations of time to event data, with 104 subjects per treatment group. The data was simulated assuming the exponential distribution with the rate parameter lambda estimated using the 8-week success rates of 69% and 47% for RBX2660 and Placebo, respectively. Using the log-rank test, the power to detect the difference between the two groups at 6 months was 99.5%.

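### The 99.5% power stated for the secondary endpoint holds only if the 8-week recurrence hazard continues unchanged to 6 months, which the protocol's own Phase 2b durability figure contradicts

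*SAP*

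**What the plan says.** SAP 6.4.2 gives the power for recurrence through 6 months as "estimated by 10,000 simulations of time to event data, with 104 subjects per treatment group". The data were generated "assuming the exponential distribution with the rate parameter lambda estimated using the 8-week success rates of 69% and 47" percent for RBX2660 and placebo. With a log-rank test, "the power to detect the difference between the two groups at 6 months was 99.5" percent. On the level it says: "These endpoints will be tested at a two-sided 0.05 significance level".

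Four other places bear on this figure:

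- SAP 4.3: "Randomization will be in a 2:1 ratio". SAP 4.4 requires 240 subjects and allows up to 270, about 180 and 90.
- Protocol 1.5.2, on Phase 2b: "The long term CDI free rate at the time of this analysis was 95.8% (91/95) for subjects successfully treated with RBX2660". Mean follow-up was 8.2 months, range 1.6 to 14.9.
- SAP 7.6.2.1 tests the sustained clinical response rate with a Pearson chi-square test at two-sided 0.05. Week-8 successes who exit before 6 months count as failures. The same section adds a log-rank comparison, for which early exits are censored.
- SAP 7.6.1.1 and 7.6.2 test the secondary endpoint only if the primary succeeds.

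**The concern.** Power at 6 months depends on how many recurrences fall between week 8 and month 6. A constant hazard makes recurrence as frequent in months 3 to 6 as in the first 8 weeks. The plan's own definitions separate a recurrence within 8 weeks from a new episode afterwards, and the sponsor's Phase 2b data show few late events. If late events are few, the simulation is crediting the trial with information that it will probably not collect.

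This is the only endpoint tested after the primary. With a stated type II risk of 0.5%, a non-significant result would read as strong evidence against a durable benefit. If the risk is really 4-20%, that reading is unsafe. The paragraph also simulates arm sizes that the trial does not use, and a test other than the chi-square test set out in SAP 7.6.2.1.

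**Working it through.** **Inputs.** 8-week success 69% and 47%, 104 per arm, log-rank, two-sided 0.05 (SAP 6.4.2). Planned sizes 160/80 (240 at 2:1) and 180/90 (SAP 4.4). Late recurrence on RBX2660 4/95 = 4.2% (Protocol 1.5.2). Six months is taken as 26 weeks.

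**1. Reproduce the stated figure.**
- Hazard ratio = ln(0.69)/ln(0.47) = 0.3711/0.7550 = 0.491.
- CDI-free at 26 weeks: 0.69^(26/8) = 0.299 and 0.47^(26/8) = 0.086.
- Expected events at 104 per arm: 104 × (0.701 + 0.914) = 168.
- Schoenfeld: √(168 × 0.25) × |ln 0.491| − 1.96 = 6.48 × 0.711 − 1.96 ≈ 2.64, so power is 99.6%.
- Simulations of the same set-up give 99.4-99.7%. The 99.5% is confirmed on its own assumptions.

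**2. What the model implies after week 8.**
- RBX2660: 1 − 0.299/0.69 = 57% of week-8 successes recur by week 26. Phase 2b reports 4.2%.
- Placebo: 1 − 0.086/0.47 = 82%. The documents give no observed counterpart.
- Events by week 8 alone: 104 × (0.31 + 0.53) = 87. The constant hazard therefore nearly doubles the events, from 87 to 168. At 104 per arm with no late events, simulated log-rank power is about 91%.

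**3. Change only the allocation.** With the constant hazard kept, log-rank power is about 99.5-99.8% at 160/80 and 99.8-99.9% at 180/90. Moving to 2:1 costs nothing.

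**4. Change the late hazard, at the planned 2:1 sizes.** The week-8 rates are held at 69% and 47%, followed by a constant low hazard from week 8 to week 26. Each case is 20,000 simulated trials, so simulation error is about 0.2 points. Only the 4.2% on RBX2660 comes from the documents. Every placebo rate, the 0% and 10% cases and the exit pattern are assumptions. Exits are 10% of event-free subjects in each arm: the log-rank test censors them and the chi-square test counts them as failures. The 10% is borrowed from the loss-to-follow-up allowance in SAP 4.4.

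| Late recurrence, RBX2660 / placebo | Log-rank 160/80 | Log-rank 180/90 | Chi-square 160/80 | Chi-square 180/90 |
|---|---|---|---|---|
| 0% / 0% | 92% | 95% | 91% | 94% |
| 4.2% / 4.2% | 91% | 93% | 88% | 91% |
| 10% / 10% | 88% | 92% | 83% | 87% |
| 4.2% / 8.5% | 94% | 96% | 93% | 95% |
| 4.2% / 15% | 97% | 98% | 97% | 98% |
| 4.2% / 4.2%, 10% exits | 90% | 93% | 79-80% | 84% |
| 10% / 10%, 10% exits | 88% | 91% | 74-75% | 80% |

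The 8.5% placebo rate is roughly what follows if the hazard ratio of 0.49 persists after week 8: 1 − 0.958^(1/0.491) ≈ 8.4%.

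**The case against.** **The Phase 2b figure is a weak anchor.** The 91/95 is a crude proportion, and some subjects had been followed for less than 6 months. The 95 appear to include successes after open-label treatment: Protocol 1.5.2 gives an overall efficacy of 88.8% in 107 subjects, and 95/107 = 88.8%. Phase 2b also excluded patients with a single recurrence, whom this trial admits (SAP section 10, Historical Data). All of this stands, and it is a reason to give a range. It cannot plausibly close a gap between 4% and 57%.

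**Late placebo recurrence is unknown.** Equal late proportions in the two arms assume little benefit after week 8. If placebo subjects recur late more often, power rises, as the 8.5% and 15% rows show. This also stands. A reader might infer that late events will not occur, or that one narrow range of power can be fixed. The documents support neither.

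**The allocation.** A reader might infer that 104 per arm, against a 2:1 trial, produces the high figure. Step 3 shows that it does not. Nor is the 99.5% an arithmetic slip: it follows from inputs that the SAP discloses.

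**The gate.** The secondary endpoint is tested only after primary success, and the two endpoints share the week-8 events. With a week-8 chi-square test as a stand-in for the gate and 4.2% late in both arms, power given primary success is about 98% (log-rank) or 95-97% (chi-square, before exits). This softens the practical consequence. It does not rescue the figure, because SAP 6.4.2 states its power without conditioning on the primary.

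**Nothing is sized on it.** The sample size comes from the primary endpoint, and no decision rule uses the 99.5%. That is correct, and it is why the remedy is limited to the text.

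**Conclusion.** The concern holds as a planning assumption that the sponsor's own data contradict. The 99.5% is correctly computed under a constant hazard, but that hazard implies about 57% late recurrence among RBX2660 successes against about 4% reported.

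With low late recurrence, unconditional power at the planned sizes is roughly 80-96%, depending on test, evaluable number and exit handling. That is a type II risk of about 4-20% in place of 0.5%. Power exceeds that range only if late placebo recurrence is assumed clearly higher than on RBX2660 (97-98% at 15% against 4.2%). It falls below only under the harshest combination tried, 10% late in both arms with 10% exits as failures (74-80%, chi-square). No low-late-recurrence case examined reaches 99.5%.

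A reader might infer that the trial is underpowered for its secondary endpoint. The documents do not support that: before exits, every case is 83% or higher. What should not stand is the near-certainty of the stated figure. The unmatched arm sizes and the unmatched test are separate faults in the same paragraph.

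**What to change.** Replace the power paragraph in SAP 6.4.2:

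- Simulate at the planned 2:1 sizes, 240 and 270 in total, in place of 104 per arm.
- Use a piecewise hazard: 69% and 47% CDI-free at week 8, then a low late rate anchored on 91/95 for RBX2660, with a stated range for placebo. Note the limits of that anchor.
- State which test is confirmatory. SAP 6.4.2 powers a log-rank test, while SAP 7.6.2.1 sets out a chi-square test that counts exits as failures. Power the chosen test under its own exit rule.
- Report power as a range with its assumptions, roughly 80-96% and higher only if late placebo recurrence is assumed clearly higher. If power given primary success is also wanted, give it separately and label it.

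The cost is one re-simulation, one rewritten paragraph, and a less favourable stated figure. Sample size and trial conduct do not change.

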6.4.3 Other Efficacy Endpoints

Other efficacy endpoints include the following:

- Baseline characteristics
- Subject fecal microbial composition at Screening, and 4-weeks, 8-weeks, 3 months and 6 months after blinded study treatment.
- Charlson Comorbidity Index at Screening, 8-week, 3-, and 6-month phone assessments.
- Cdiff32 questionnaire at Screening, Week 1, 4, 8, month 3 and 6
- ATLAS score for CDI severity of qualifying CDI event.
- Recurrence of CDI within 8 weeks of unblinded (open-label) RBX2660 treatment in Placebo subjects who were documented blinded study treatment failures.
- Recurrence of CDI within 8 weeks of unblinded (open-label) RBX2660 treatment in subjects who received a blinded dose of RBX2660.
- Occurrence of CDI through 6 months in all subjects receiving a single dose of RBX2660.
- Concentration of vancomycin resistant enterococcus in stool samples for subjects who were carriers at baseline.
- Presence of *C. difficile* in stool samples at Screening, and 4-weeks, 8-weeks, 3 months and 6 months after blinded study treatment.

6.5 Safety Variables

All the safety analyses will be based on the safety population; see Section 6.3.4 in this document.

6.5.1 Safety Endpoints

- Number of adverse events per subject
- Timing of attributable adverse event post-treatment exposure (treatment emergent adverse event TEAE)
- Duration of TEAE
- Relatedness of TEAE
- Severity of TEAE
- Causality of TEAE to IP, enema, *C. difficile* or prior condition Number of each of the following through 8 weeks post blinded treatment: death, septic shock, toxic megacolon, colonic perforation, emergency colectomy, and ICU admission.
- Onset of new chronic conditions relative to blinded treatment administration.

6.5.2 Extent of Exposure to Study Treatment

The number and proportion (RBX2660 vs Placebo) of enemas administered for each subject will be summarized using descriptive statistics by treatment arm at each study enema administration (blinded and unblinded). Time between study enema administrations will be summarized using descriptive statistics for both blind and unblinded enemas. Additional analysis will be done for those subjects who received both Placebo and RBX2660 enemas.

6.5.3 Adverse Events

An adverse event (AE) is any untoward medical occurrence associated with the use of IP, whether or not the event is considered product-related. Preexisting conditions that worsen in frequency, intensity or character of the condition during study participation will be recorded as an AE. AEs will be recorded for each subject from the day of enrollment through the 6-month

telephone assessment. Serious adverse events (SAEs) will be recorded for each subject from the day of enrollment through the duration of the study.

6.5.3.1 Adverse Event Dictionary

AEs and SAEs will be classified by the current Medical Dictionary for Regulatory Activities (MedDRA) version. The verbatim term recorded by the investigator will be mapped in MedDRA and system organ class (SOC), high level group term (HLGT), high level term (HLT), preferred term (PT), and lower level term (LLT) will be attached to the clinical database. Tables and listings will present data at the SOC and PT level.

6.5.3.2 Adverse Event Severity

Severity of AEs will be graded as mild, moderate, severe, or potentially life-threatening. The severity grade of events for which the investigator did not record severity will be categorized as “Unknown” for tabular summaries and data listings, and will be considered the least severe for the purposes of sorting for data presentation. For summaries by severity grade, if a subject has multiple events occurring in the same SOC or PT, then the most severe event will be selected.

6.5.3.3 Relationship of Adverse Events to Study Treatment

Relationship of an AE to the Investigational Product (IP), the enema procedure, *C. difficile* disease, and a preexisting condition will be classified by the investigator as definite, probable, possible, or unrelated. Related events will include AEs that are classified as definitely, probably, or possibly related. IP includes both the Placebo and RBX2660 enemas.

6.5.3.4 Treatment-Emergent Adverse Events

Adverse events will be considered treatment-emergent adverse events (TEAE) according to the following algorithm:

- If the complete onset date of an AE is known, then:
 - If AE onset date is prior to initial treatment date, then the AE will not be considered treatment-emergent.

- If AE onset date occurs on or after initial treatment date, then the AE will be considered treatment-emergent.
- If AE onset date is partially known, then:
 - If day is unknown, and month/year occurs on or after first enema month/year, then AE will be considered treatment-emergent. Otherwise, AE will not be considered treatment-emergent.
 - If month/day is unknown, and year occurs on or after first enema year, then AE will be considered treatment-emergent. Otherwise, AE will not be considered treatment-emergent.

6.5.4 Other Observations Related to Safety

6.5.4.1 Solicited Adverse Events

The following list of anticipated adverse events are solicited from subjects via the Subject Diary from the date of enrollment through the 7th day after receiving the randomized study treatment. For those subjects who receive an unblinded RBX2660 enema, these events are again collected in a new post-treatment Subject Diary from the day of the unblinded RBX2660 enema to the 7th day after receiving the unblinded RBX2660 enema:

- gas (flatulence)
- abdominal distension or bloating
- rectal irritation or pain
- chills/severe shivering
- abdominal pain or cramping
- increased diarrhea
- constipation
- rectal bleeding
- nausea
- vomiting
- fever $\geq 37.8^{\circ}\text{C}$ ($\geq 100.0^{\circ}\text{F}$)

Frequency and severity of the solicited AEs will also be captured in the Subject Diary.

6.5.4.2 Major Complications of CDI Events

Frequencies of major complications of CDI including death, septic shock, toxic megacolon, colonic perforation, emergency colectomy, or ICU admission will be collected through the 6-month telephone assessment.

6.5.4.3 Hospitalizations for Recurrent CDI

Details regarding hospitalizations due to CDI, including admission and discharge date/time, reason for admission, whether the subject was admitted to an ICU, and ICU admission and discharge date/time (if applicable), will be collected following both the blinded and unblinded study enemas.

7 STATISTICAL ANALYSIS

7.1 Disposition of Subjects

A summary table will present subject disposition for all subjects enrolled. The table will show the number of subjects enrolled (consented), the number of enrolled subjects not randomized, followed by the number of subjects randomized for each treatment group and lastly the number of subjects randomized and treated. The proportion of randomized subjects in each treatment group and overall who complete the study and who discontinue the study will be presented. Separately, a table or listing will be created to document the subjects that are included in each analysis population; ITT, mITT, PP and SP.

Discontinuation will be categorized by reason as a percentage of the number of subjects in each analysis population and overall. Additionally, subjects who were successfully treated but withdraw prior to the 8-week primary endpoint evaluation will be identified along with the reason for withdrawal to document which analysis population(s) to which they contribute.

7.2 Protocol Deviations

Protocol deviations will be documented in the clinical database. The information available will be summarized by treatment arm and deviation type and listed by individual site.

7.3 Baseline Assessments

Baseline assessments are collected within 30 days before or on the day of study treatment administration. Summaries for age by group (< 65 and \geq 65), sex, ethnicity, and race will be provided by analysis group and treatment arm. Baseline height, weight and employment status will also be summarized by analysis group and treatment arm. CDI history will be summarized by total number of episodes experienced prior to blinded treatment. Additionally, the following will be summarized for each episode of CDI: duration (days), treatment administered, hospitalization with duration (if applicable) and available *C. difficile* test results. Additionally, the severity of the qualifying CDI episode will be documented for each subject by ATLAS score and the baseline comorbidities will be scored for each subject using the Charlson Comorbidities Index.

The following baseline assessments will be provided in summary table and listings by treatment arm:

- Medical history
- CDI history
- Laboratory testing (hematology)
- Vital signs (systolic/diastolic blood pressure [mmHg], pulse rate [beats/min], respiration rate [breaths/min], temperature [$^{\circ}$ C])

7.4 Demographic and Other Baseline Characteristics

All baseline summaries will include the ITT, mITT and PP population and will be provided by treatment arm. Descriptive statistics (number of subjects [N], mean, standard deviation [SD], median, interquartile range [IQR], minimum, and maximum for continuous variables and number

of subjects [N] and the percentage for categorical variables) will be provided for all baseline measures.

7.5 Prior and Concomitant Therapy

The current World Health Organization (WHO) Drug Dictionary will be used to classify medications by preferred term and WHO Anatomical Therapeutic Chemical (ATC) at the highest level of ATC. Listings of all concomitant medications will be made by WHO ATC classification of ingredients and by preferred term tabulated by each treatment arm. All listings of usage of medications will be based on the Safety population.

7.6 Analysis of Efficacy

7.6.1 *Analyses Supporting the Primary Efficacy Endpoint*

7.6.1.1 *Treatment Success*

A hierarchical, closed-testing procedure will be utilized for the primary endpoint and secondary endpoints. Analyses of the single primary endpoint, recurrence of CDI within 8 weeks of blinded treatment, will be analyzed as the proportion of treatment success of Group A Placebo (P_{PLA}) and Group B RBX2660 (P_{RBX}). This analysis will be performed on the ITT, mITT and PP populations, with the mITT being the analysis of import for reporting purposes.

The primary efficacy analysis will be a Bayesian hierarchical model which formally incorporates data from the previous Phase 2B study (Protocol 2014-01) of RBX2660. Study success will be declared if the posterior probability of superiority exceeds 0.99943 at the first two interim analysis. If the trial continues to the maximum enrollment, the success criteria will be chosen so that the overall alpha is a nominal 0.00125. Success at this level is considered appropriate for approval based on results from a single study. If success at this level is not met at the final analysis, success may also be declared if the posterior probability exceeds 0.97706. Success at this secondary threshold still constitutes a successful study, although it may not be sufficiently strong evidence to request regulatory approval based on a single study without further FDA discussion. Details regarding the analysis can be found in Section 10 (Bayesian Analysis Plan).

The secondary endpoints will be analyzed using a hierarchical testing approach if sufficient evidence is found to claim study success.

The primary efficacy analysis will be conducted when all subjects in each group reach their 8-week assessment following blinded treatment or early termed from the study. Full study results in the form of a final analysis and report will be completed once the last subject has completed the 6-month telephone assessment, at which time the study will be considered complete. This includes subjects receiving unblinded RBX2660 due to a documented treatment failure.

